The SADT-a predicts SAD in patients with asthma using a single criterion – wheezing at rest – along with certain basic patient characteristics, such as age, sex, age at diagnosis, and Body Mass Index (BMI); this is the bronze model (area under receiver operation characteristic curve (AUC) 0.74 and positive likelihood ratio (LR+) 2.3). Its ability to accurately identify SAD in asthma is greatly enhanced with the use of spirometry, which evaluates lung function by measuring air volume and flow during breathing; this represents the silver model (AUC 0.87, LR+ 5.0). The results from spirometry primarily include the FEV_1 % predicted. The diagnostic precision further improves with the incorporation of oscillometry, marking the gold model (AUC 0.96, LR+ 12.8). This technique assesses lung function by measuring airflow resistance and includes parameters like the resistance difference between 5 and 20 Hz (R5-R20) and reactance area (AX)⁸.

The current study aims to adapt the original 63-item SADT questionnaire for dedicated use in COPD by reducing the number of items and enhance its efficiency in identifying SAD in individuals with COPD (the SADT-c). This process will follow the approach previously used for asthma⁸. We will assess the predictive value of SADT-c. Additionally, we will determine whether the bronze model of SADT-a is similarly predictive for SAD in COPD as is the bronze model of SADT-c.

Since oscillometry is not standardized in clinical practice, and the access and quality of spirometry is low¹¹, it would be of great value to determine whether oscillometry and spirometry are equally effective in the diagnostic work-up of respiratory symptomatic patients in primary care. Spirometry requires collaboration of the patient to perform a forced expiratory maneuver and well-trained Version 1.0, 19 April 2024 9 of 27

staff¹², whereas oscillometry is easy to perform as no training and limited effort of the patient is required (45 seconds of tidal breathing) and limited training of the staff¹³. In order to compare the effectiveness of spirometry and oscillometry, spirometry and oscillometry measurement will be interpreted by a panel of experts to provide a triage diagnosis. The previously developed machine learning AC/DC tool will be used to explore its diagnostic accuracy using oscillometry and spirometry results¹⁴.

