6. METHODS

6.1 Study endpoints

6.1.1 Main study endpoint

The primary endpoint is the predictive value of SADT-c for detecting SAD in patients with COPD.

Required variables:

- Diagnosis of Asthma/COPD service
- SAD status defined as R5–R20 > upper limit of normal (ULN)¹
- SADT question results
- Patient characteristics
 - o Age
 - o Sex
 - o Height
 - Body Mass Index (BMI)
 - Age at diagnosis
- Oscillometry and spirometry results

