8.1 Primary study parameter(s)

The primary endpoint is the predictive value of SADT-c for SAD in COPD. The statistical hypothesis for the primary objective is that the predictive value of SADT-c is above the lower limit of the confidence interval of predictive value of SADT-a (AUC 0.74, LR+ 2.3 for the SADT-a bronze model). The hypothesis will be tested at a 2-sided significance level of 0.05.

For the analysis of this primary endpoint, the following population is defined:

- All participants that have a prior or novel COPD (triage) diagnosis, and
- Do not have an asthma, asthma-COPD overlap syndrome, missing or other diagnosis, and
- Have filled in the SADT-c questionnaire.

The presence of SAD will be based on oscillometry results. A resistance difference between 5 and 20 Hz (R5-R20) cutoff of 0.07 kPa x s x L⁻¹ will be used to define the presence of SAD¹⁵.

Analysis will be performed as done earlier for the development of SADT for asthma⁸. In short, to assess the predictive value of SADT-c we first will select the most important SADT items (secondary study parameter). Regression analysis will be used to select SADT items that show a relation with SAD in the expected direction based on the content validity of the items. In a next step the most important SADT items for SAD group will be selected by using logistic regression models. Prediction models using bootstrapping resampling will be used. In addition to the individual SADT items, also patient characteristics, such as age, sex, and height, BMI, will be considered as independent predictors in the model.

Selected key SADT items will be used together with available clinical information to build logistic regression models to predict the SAD group. Three levels of clinical information will be considered resulting in three regression models:

- Bronze: Basic patient characteristics (such as age, sex, age at diagnosis, BMI, or other)
- Silver: Spirometry test results (FEV₁ % predicted)
- Gold: Oscillometry test results (R5-R20 and reactance area (AX)).

For each model the area under the receiver operating characteristic curve (AUC), positive likelihood ratio (LR+) and sensitivity and specificity will be calculated, using a probability cut-off of 0.5 to indicate predicted SAD.

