8.2 Secondary study parameter(s)

SADT-c

To determine whether bronze model SADT-a is predictive for SAD in COPD, the steps described in section 8.1 will be followed. The AUC, LR+ and sensitivity and specificity will be calculated and reported.

To assess the agreement between SADT-c and disease parameters, the steps described in section 8.1 will be reported. Logistic regression analysis results will be reported.

To assess the content validity and reliability of the SADT-c, 10-15 patients with COPD and SAD will be invited for a cognitive interview. Results will be presented in a descriptive way.

To evaluate how SADT-c and SADT-a compare in detecting SAD in COPD the predictive values of the various SADT-c and SADT-a models will be compared.

In case the SADT-c has a significantly reduced predictive value as compared to the SADT-a, new items derived from the cognitive interviews will be added, if any. The amended questionnaire will subsequently be reinvestigated using the same protocol, in the same population (ie. 100 patients with COPD participating in the SCOOP study).

Oscillometry vs spirometry

To assess the agreement between oscillometry and spirometry, triage diagnoses as determined by the expert panel will be compared. Cohen's kappa or comparable statistics will be used to compare the outcomes. Additional analysis will be done adjusted for difficulty of diagnosis and the agreement between panel members. In addition, subgroup analysis will be performed based on the level of agreement between panel members.

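### The primary hypothesis gives two benchmarks, AUC and LR+, without saying which decides, and at the plan's own cut-off and SAD prevalence the two are expected to disagree

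*Protocol*

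**What the plan says.** Protocol section 6.1.1 defines the endpoint without a measure: "The primary endpoint is the predictive value of SADT-c for detecting SAD in patients with COPD". Section 8.1 repeats it and adds the hypothesis that "the predictive value of SADT-c is above the lower limit of the confidence interval of predictive value of SADT-a (AUC 0.74, LR+ 2.3", with both figures labelled as those of the SADT-a bronze model. It then says: "The hypothesis will be tested at a 2-sided significance level of 0.05".

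Under the same heading, "Three levels of clinical information will be considered resulting in three regression models": bronze (patient characteristics), silver (adding FEV1 % predicted) and gold (adding oscillometry). Then "For each model the area under the receiver operating characteristic curve (AUC), positive likelihood ratio (LR+) and sensitivity and specificity will be calculated", with a predicted probability of 0.5 as the cut-off for calling SAD present.

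In section 8.2, "the predictive values of the various SADT-c and SADT-a models will be compared". If SADT-c turns out significantly worse than SADT-a in predictive value, items from the interviews, if any, are added and the amended questionnaire is investigated again in the same 100 patients.

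**The concern.** The hypothesis is singular and has one alpha, but its benchmark has two parts. The protocol does not say whether SADT-c must beat the AUC limit, the LR+ limit, either one or both. Nor does it state outright that the bronze SADT-c model is the one tested.

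This would matter little if the two measures moved together. They need not. AUC does not depend on prevalence or on a cut-off. LR+ at a fixed probability cut-off depends strongly on prevalence. When most patients have SAD, a cut-off of 0.5 classifies nearly everyone as positive, so specificity falls and LR+ is pulled towards 1.

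At stake is whether the trial concludes that SADT-c can be used in COPD. The decision in section 8.2 to amend the questionnaire rests on the same undefined term.

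**Working it through.** **Inputs from the protocol**
- SADT-a benchmarks: bronze AUC 0.74, LR+ 2.3 (sections 1 and 8.1); silver AUC 0.87, LR+ 5.0 (section 1).
- SAD prevalence in COPD: 74% to 83% (section 4.4).
- Cut-off for predicted SAD: probability 0.5 (section 8.1).
- Patients with COPD: 100 (section 4.4).

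**Assumptions.** The risk score is normal with equal variance in both groups, and predicted probabilities are calibrated. The protocol prints no confidence limit for either SADT-a measure.

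**Formulas.** Let the score be N(0,1) without SAD and N(d,1) with SAD, and let π be the prevalence.
- d = √2 × Φ⁻¹(AUC)
- The predicted probability reaches 0.5 at score c = d/2 − ln(π/(1−π))/d
- Sensitivity = Φ(d − c); false-positive rate = Φ(−c); LR+ = sensitivity / false-positive rate

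**The plan's own pair first.** SADT-a's AUC 0.74 and LR+ 2.3 cannot be reproduced exactly, because the protocol gives neither the SAD prevalence nor the cut-off in the asthma study. At π = 0.50 the formula gives d = 1.414 × 0.643 = 0.910, c = 0.455, sensitivity 0.675, false-positive rate 0.325 and LR+ 2.08. That is near 2.3, so the pair is plausible for a roughly balanced population.

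**The same AUC at the COPD prevalences**
- π = 0.74: ln(0.74/0.26) = 1.046; c = 0.455 − 1.046/0.910 = −0.695; sensitivity Φ(1.605) = 0.946; false-positive rate Φ(0.695) = 0.756; LR+ = 1.25.
- π = 0.83: ln(0.83/0.17) = 1.586; c = 0.455 − 1.586/0.910 = −1.288; sensitivity Φ(2.198) = 0.986; false-positive rate Φ(1.288) = 0.901; LR+ = 1.09.

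| True AUC | Prevalence | Sensitivity | Specificity | LR+ |
|---|---|---|---|---|
| 0.74 | 74% | 0.946 | 0.244 | 1.25 |
| 0.74 | 83% | 0.986 | 0.099 | 1.09 |
| 0.80 | 74% | 0.930 | 0.388 | 1.52 |
| 0.80 | 83% | 0.973 | 0.231 | 1.26 |
| 0.87 | 74% | 0.927 | 0.556 | 2.09 |
| 0.87 | 83% | 0.963 | 0.421 | 1.66 |

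**AUC needed for LR+ 2.3.** At 74%, AUC 0.887: d = 1.712, c = 0.856 − 0.611 = 0.245, LR+ = Φ(1.467)/Φ(−0.245) = 0.929/0.403 = 2.3. At 83%, AUC 0.921: d = 1.997, c = 0.998 − 0.794 = 0.204, LR+ = Φ(1.793)/Φ(−0.204) = 0.963/0.419 = 2.3. Both exceed the asthma silver value of 0.87.

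**The unprinted LR+ limit.** The hypothesis uses the lower confidence limit, not 2.3 itself. A SADT-c with AUC 0.74 lies below any LR+ limit above 1.25 (at 74%) or above 1.09 (at 83%). With AUC 0.80 the corresponding values are 1.52 and 1.26.

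**Sampling at N = 100.** In 4,000 simulated data sets per setting with true AUC 0.80, the estimated AUC exceeded 0.74 while LR+ was 2.3 or less in 86% (prevalence 74%) and 85% (prevalence 83%). With limits assumed at 0.68 for AUC and 1.8 for LR+, AUC exceeded its limit and LR+ did not in 83% and 95%. These figures compare point estimates, not formal tests, and ignore model-fitting optimism.

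**What the readings amount to.** In this setting LR+ is the harder hurdle. An either-measure rule behaves much like AUC alone, and a both-measures rule much like LR+ alone. The unstated rule therefore decides the answer.

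**The case against.** Section 8 of the protocol calls itself a summary and leaves technical detail to a SAP that is not shown. The benchmark is labelled bronze, and the Introduction describes a comparison of the two tools' bronze models. On that reading the model is settled and only the choice of measure is open, which a SAP could fix.

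Much of this stands. Bronze against bronze is the natural reading, and the gap over the model is one of explicit wording. The choice of measure is different. The protocol itself states the hypothesis, the benchmark and the alpha, and the rule that decides the primary objective is more than technical detail when its two candidate measures point in opposite directions.

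A reader might go further and infer that two measures and three models give six comparisons, each tested at full alpha, with an inflated error rate. The protocol does not say this. It states one hypothesis, and the measures for each model are calculated, not declared as tests. Error rates for an any-of-six rule also require every comparison to sit exactly at its benchmark. That is implausible for LR+, as shown above, and for a gold model that contains R5-R20, the variable defining SAD, when set against a bronze benchmark. In a simulation with AUC at its limit (0.66 to 0.74) and the LR+ limit assumed to be 1.5 or 1.8, LR+ passed in 0.0% of trials. AUC or LR+ passed in 2.3% to 3.0%, no more than AUC alone.

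A reader might also infer that a silver model could pass the bronze benchmark on the strength of FEV1. No section prescribes that cross-level comparison, and the Introduction gives silver its own figures: "this represents the silver model (AUC 0.87, LR+ 5.0". Nor does listing oscillometry among the primary variables in section 6.1.1 show that the gold model decides, since R5-R20 is needed to define SAD in any case.

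**Conclusion.** The point holds in this form: section 8.1 gives two benchmark measures for one primary hypothesis and no rule for which decides, while the model under test is left to a label. The measures are expected to give opposite verdicts. A SADT-c that matches SADT-a exactly on AUC has an expected LR+ of about 1.25 to 1.09 against a benchmark estimate of 2.3.

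The size rests on the equal-variance binormal model, on calibrated probabilities, and on the 74% to 83% prevalence taken from earlier studies. It shrinks if SAD is much less common in this primary-care sample (LR+ 2.08 at 50%) or if the SADT-a lower limit for LR+ is close to 1. The missing rule does not depend on these assumptions. The documents do not support a claim of inflated type I error. The sponsor should correct the text before database lock.

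**What to change.** In protocol section 8.1, and in the SAP, state one deciding comparison, for example: the primary test compares the AUC of the bronze SADT-c model with the SADT-a bronze AUC benchmark, at two-sided 0.05. LR+, sensitivity and specificity at the 0.5 cut-off, and all silver and gold results, are secondary and are compared only with the SADT-a model of the same level.

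In section 8.2, use the same bronze AUC comparison to decide whether predictive value is significantly reduced.

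The cost is a change of wording before database lock, with no new patients or data. The small downside is that a good LR+, or a good silver or gold result, cannot by itself support the primary claim.

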4.4 Sample size calculation

To determine whether Small Airway Dysfunction Tool for COPD (SADT-c) can be used in patients with COPD to detect Small Airways Disease (SAD) a prediction model will be used. To estimate the required sample size for a prediction study, a well-known rule of thumb is to ensure at least 10 events for each predictor parameter.

Previous studies indicated a prevalence of SAD in patients with COPD ranging from $74\%^{15}$ to $83\%^{16}$. The final prediction model previously developed for patients with asthma included four variables in the bronze model and 7 variables in the gold model⁸. Therefore, we assume that we will have enough statistical power when we include 100 patients diagnosed with COPD in the current study.

5. SCOOP procedures

The SCOOP study will be integrated in the visits of the Asthma/COPD service for primary care at the study sites. General Practitioners (GPs) can refer individual patients (≥18 years of age) who are suspected to have obstructive airway disease (OAD) such as asthma, Chronic Obstructive Pulmonary Disease (COPD), asthma-COPD overlap (ACO) or present with pulmonary symptoms of unknown origin¹⁷. Visits can be for initial diagnosis of the OAD or for (yearly) follow-up of the disease.

In preparation for the regular asthma/COPD service visit the patient will receive questionnaires to complete, i.e.: the Asthma Control Questionnaire (ACQ), the Clinical COPD Questionnaire (CCQ) and a medical history questionnaire assessing gender, age, age of onset, family history, symptoms, exacerbations (oral corticosteroids or antibiotics use), allergy and other stimuli-provoking symptoms, medication, occupation, and smoking history.

During the visit the patient is assessed by a trained lung function technician. The following measurements are collected: Body mass index (BMI), evaluation and if needed instruction of inhalation technique (according to the Dutch Inhalation Medication Instruction School guidelines), spirometry (according to international guidelines).

Besides the regular assessments, the following assessments will be added for the SCOOP-study:

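### With 74–83% SAD expected, reading LR+ at a fixed probability of 0.5 pulls it towards 1, so the asthma LR+ of 2.3 is not a usable benchmark in the primary hypothesis

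*Protocol*

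**What the plan says.** Section 8.1 of the protocol sets the primary hypothesis as follows: "the predictive value of SADT-c is above the lower limit of the confidence interval of predictive value of SADT-a", with the reference values given in brackets as "AUC 0.74, LR+ 2.3 for the SADT-a bronze model". It adds: "The hypothesis will be tested at a 2-sided significance level of 0.05". The lower limit itself is not given anywhere in the protocol.

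The same section lists the measures, "For each model the area under the receiver operating characteristic curve (AUC), positive likelihood ratio (LR+) and sensitivity and specificity will be calculated", and fixes the classification rule for all of them: "using a probability cut-off of 0.5 to indicate predicted SAD". An R5–R20 cut-off of 0.07 kPa·s/L "will be used to define the presence of SAD".

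Section 4.4 gives the expected frequency of the outcome: "Previous studies indicated a prevalence of SAD in patients with COPD ranging from" 74% to 83%. The 74% figure and the 0.07 cut-off cite the same source, so the high prevalence belongs to the SAD definition used in the primary analysis.

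Section 8.2 evaluates the SADT-a bronze model in COPD by the steps of 8.1 and compares the two tools. It provides for new questionnaire items if SADT-c has significantly lower predictive value than SADT-a.

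**The concern.** A logistic model with an intercept has a mean predicted probability, in the data it was fitted to, equal to the observed proportion with the outcome. Here that mean would be about 0.74 to 0.83. If discrimination is modest, few patients fall below 0.5, so almost all are classified as having SAD. Specificity collapses and LR+ approaches 1, however well the score ranks patients.

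LR+ stands beside AUC as a reference value in the primary hypothesis, and its benchmark comes from a different disease population. The two measures could therefore point in opposite directions for a tool that is just as good as SADT-a. The protocol does not say which would decide. Sensitivity and specificity at 0.5 would also give a poor picture of the tool: of about 17 to 26 patients without SAD among 100, only about 2 to 6 would be classified as negative.

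**Working it through.** **Inputs.** Cut-off 0.5 and benchmark AUC 0.74 with LR+ 2.3 (section 8.1); SAD prevalence 74–83% and 100 COPD patients (section 4.4); silver AUC 0.87 with LR+ 5.0 and gold AUC 0.96 with LR+ 12.8 (section 1).

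**Assumption.** A calibrated score whose distribution is normal with equal variance in patients with and without SAD. The protocol gives no score distribution.

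**Formulas.**
- d = √2 × Φ⁻¹(AUC) = 1.414 × 0.643 = 0.910
- L = logit(prevalence) − logit(cut-off); at a cut-off of 0.5 the second term is 0
- sensitivity = Φ(d/2 + L/d); 1 − specificity = Φ(−d/2 + L/d)
- LR+ = sensitivity / (1 − specificity)

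**The plan's own figure.** LR+ 2.3 cannot be reproduced, because the protocol gives neither the SAD prevalence nor the cut-off behind it. Under the assumption above, AUC 0.74 read at 0.5 gives LR+ 2.08 at 50% prevalence and 2.3 at about 46%. So 2.3 is plausible for a roughly balanced sample. The silver and gold values would need about 39% and 33%, so the model is only an approximation.

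**AUC 0.74 at cut-off 0.5.** For 74%: L = ln(0.74/0.26) = 1.046 and L/d = 1.150. Sensitivity is Φ(1.605) = 0.946, 1 − specificity is Φ(0.695) = 0.756, and LR+ is 0.946/0.756 = 1.25. The other rows follow in the same way.

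| Prevalence | Sensitivity | Specificity | Called SAD | LR+ |
|---|---|---|---|---|
| 50% | 0.675 | 0.675 | 50% | 2.08 |
| 60% | 0.816 | 0.504 | 69% | 1.64 |
| 74% | 0.946 | 0.244 | 90% | 1.25 |
| 78% | 0.968 | 0.175 | 94% | 1.17 |
| 83% | 0.986 | 0.099 | 97% | 1.09 |

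Correctly classified negatives among 100 patients: 26 × 0.244 = 6.3 at 74% and 17 × 0.099 = 1.7 at 83%.

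**What 2.3 would require.** At a cut-off of 0.5, an AUC of about 0.89 (74% prevalence) to 0.92 (83%). Both exceed the AUC that the asthma tool reached with spirometry added: "this represents the silver model (AUC 0.87, LR+ 5.0").

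**Silver and gold at 0.5.** With the asthma AUCs, silver would give LR+ 2.09 to 1.66 against 5.0, and gold 4.59 to 3.53 against 12.8.

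**Sampling variation.** In 2,000 simulated studies of 100 patients per setting, a logistic model with one or five predictors (true AUC 0.74) was refitted and read at 0.5 in the same data. Median LR+ was 1.27 and 1.38 at 74% prevalence, and 1.10 and 1.19 at 83%. LR+ reached 2.3 in 0.7% and 2.1% of studies at 74%, and in 0.3% and about 0.6% at 83%.

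**Cut-off equal to prevalence.** Then L = 0, sensitivity = specificity = Φ(0.455) = 0.675, and LR+ = 0.675/0.325 = 2.08 at any prevalence. LR+ 2.3 would need a cut-off of about 0.77 at 74% or 0.85 at 83%.

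**The case against.** Several points on the other side stand.

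- **A reader might infer that LR+ 2.3 is impossible.** It is not. The result depends on the score shape. For a two-valued score, AUC 0.74 means sensitivity − (1 − specificity) = 2 × 0.74 − 1 = 0.48. The most favourable such score that 0.5 still separates has LR+ 0.74/0.26 = 2.85 at 74% prevalence and 0.876/0.396 = 2.21 at 83%. That is an extreme case, since the planned model adds several patient characteristics.
- **The formal criterion is not 2.3.** It is the lower confidence limit of the SADT-a value, which the protocol does not give. Failure on LR+ is therefore probable but not demonstrated.
- **A reader might infer that the comparison of SADT-a with SADT-c is biased.** Sections 6.1.2 and 8.2 assess both tools for SAD in COPD, and 8.2 sends SADT-a bronze through the steps of 8.1. Both LR+ values are then pulled towards 1. The contrast is compressed, but neither tool is favoured.
- **A reader might infer that prevalence would trigger the amendment rule.** That follows only if SADT-a in that rule means the published asthma value. Section 8.2 does not say so, and the rule comes directly after the within-COPD comparison.
- **The prevalence comes from cited studies.** About half of the COPD patients here are to be newly diagnosed in primary care, and the problem shrinks if fewer have SAD. Still, 74–83% is the protocol's own planning assumption, and LR+ is already 1.64 at 60%.

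Using the same method as in asthma is not a full answer. The same cut-off does not give a comparable LR+ when prevalence differs. The SAP could settle the matter before database lock, but the protocol has already fixed the 0.5 rule and the benchmark.

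**Conclusion.** The concern holds for LR+, sensitivity and specificity read at 0.5, and for using the asthma LR+ as a reference in the primary hypothesis. At the protocol's expected prevalence, a SADT-c with the benchmark AUC would show LR+ of about 1.25 to 1.09 and specificity of about 24% to 10%. It would meet the hypothesis on LR+ only if the unstated limit were close to 1. This rests on a calibrated, roughly binormal score and on 74–83% SAD in the analysis set.

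It does not follow that the primary analysis as a whole must fail, because AUC does not depend on the cut-off. A better threshold also does not rescue 2.3 as a pass mark: at a cut-off equal to the prevalence the same model gives about 2.1.

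**What to change.** In section 8.1, and carried into the SAP before database lock:

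1. State that AUC alone decides the primary hypothesis. Report LR+ with its confidence interval descriptively, not against 2.3.
2. Calculate LR+, sensitivity and specificity at a cut-off equal to the observed SAD prevalence in the analysis set. Use the same rule for SADT-a and SADT-c, and repeat it inside each bootstrap sample.
3. Keep 0.5 as a secondary display for comparability with the asthma work.

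In section 8.2, state that the amendment rule uses the AUC comparison of the two tools within COPD.

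The cost is a few sentences, with no extra data. The downside is that the main threshold may differ from the one used for SADT-a in asthma, which is why both are shown. Step 1 protects the primary conclusion; steps 2 and 3 make the secondary accuracy figures informative.
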